2.4 Exclusion Criteria

1. Diagnostic Read code for the following chronic lower respiratory conditions ever:
 - a. Pulmonary sarcoidosis
 - b. Hypersensitivity pneumonitis
 - c. Malignancy of the lungs
 - d. Interstitial Lung Disease
 - e. Cystic fibrosis
2. Chronic treatment with oral corticosteroids

³ In the UK, a diagnosis of COPD under the terms of the Quality Outcome Framework of the GP General Medical Services Contract requires a diagnostic procedure for COPD following NICE guidelines². This includes the requirement that airflow obstruction is confirmed by post-bronchodilator spirometry as from 1st April 2008. <http://www.hscic.gov.uk/qof>

(Patients with a concurrent diagnosis of asthma will be included)

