1. BACKGROUND AND RATIONALE

1.1 Background

In the UK, 4.5% of all people aged over 40 are estimated to live with diagnosed Chronic Obstructive Pulmonary Disease (COPD), based on Read codes recorded in Electronic Medical Records (7). The UK is among the top 20 countries for COPD mortality worldwide (8).

COPD is a heterogeneous condition with patients showing varying clinical and pathophysiological features. The identification of COPD phenotypes with distinct characteristics may allow targeted treatment strategies directed towards specific biological pathways.

Eosinophilic inflammation is thought to be a characteristic feature of asthma rather than COPD. However, studies have shown that there is a subset of COPD patients with eosinophilic airway inflammation, even after exclusion of patients with any features of asthma (1). Interestingly, this subset of patients with COPD exhibit the greatest response to corticosteroid treatment (4, 9) and tailoring of therapy based on sputum eosinophil counts is more effective in reducing exacerbations than treatment according to traditional guidelines (5). This suggests that there is a sub-phenotype of COPD with an eosinophilic type of airway inflammation similar to that observed in patients with asthma (10).

In a study performed in patients with COPD from the general population of Denmark, blood eosinophil levels above $0.34 \times 10^9 / L$ were associated with a 1.76-fold increased risk for severe COPD exacerbations requiring hospitalization and with a 1.15-fold increased risk for exacerbations not requiring hospital admission (11).

Previous work conducted at OPRI confirmed the increased risk of exacerbations with high blood eosinophil counts in real-life UK patients with COPD from the Optimum Patient Care Research Database (OPCRD) when using a higher cut-point of $\geq 0.45 \times 10^9 / L$, observed in 10% of the population (submitted for publication). However, the association was limited to patients who were not actively smoking. Ex-smokers with high blood eosinophil counts showed a 32% higher rate of exacerbations than ex-smokers with normal eosinophil counts. The association was found in patients treated with ICS and in patients in GOLD groups B to D, and was not influenced by any prior recording of asthma.

[figure not shown]

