3.2.4 Health care Resource Use

The following outcomes of HRU are described in the baseline year and outcome year in patients with HES data available.⁴

1. Physician office visits:
 - a. Total number of General Practice (GP) surgery consultations
 - b. Number of COPD-related GP consultations
2. Outpatient visits:
 - a. Total number of referrals to specialist
 - b. Number of referrals to specialist for COPD or other lower respiratory conditions
3. Accident & Emergency (A&E) attendances / out of hours services:
 - a. Total number of A&E attendances
 - b. Total number of GP out-of-hours consultations
 - c. Number of A&E attendances for COPD or other lower respiratory conditions
4. Hospital admissions: Number of hospital admissions (spells):
 - a. For all-causes
 - b. With COPD exacerbations (ICD-10 J44.0 or J44.1) as primary diagnosis
 - c. With COPD exacerbations ICD-10 J44.0 or J44.1 as secondary / subsidiary diagnosis and respiratory conditions (ICD-10 J00-J99) as primary diagnosis
5. Number of COPD-related drug prescriptions:
 - a. Fixed dose combination (FDC) of inhaled corticosteroids (ICS) and Long-acting β 2-agonists (LABA)
 - b. Stand-alone ICS
 - c. Stand-alone LABA
 - d. Stand-alone LAMA
 - e. FDC LAMA / LABA
 - f. Short-acting β 2-agonists (SABA)
 - g. Short-acting Muscarinic Antagonists (SAMA)
 - h. Theophylline
 - i. Oral corticosteroids
 - j. Antibiotics prescribed with lower respiratory consultation Read code
6. Total number of drug prescriptions for all causes

Outcomes are described as mean numbers (\pm standard deviation (SD)) and as categorical variables (0, 1, 2, 3, ≥ 4 for outpatient visits, A&E attendances and hospitalisations; 0, 1-4, 5-8, 9-12, 13-24, ≥ 25 for GP consultation; ≥ 1 prescription (yes/no) for drugs)

⁴ Events occurring at index date are counted in the baseline year, except medication prescriptions which are counted in the outcome year

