3.4 Statistical Methods – General Aspects

Summary statistics are provided for all baseline and outcome variables, for the complete dataset and by comparison groups. For continuous variables, these include:

- Sample size (n)
- Percentage non-missing
- Mean \pm Standard Deviation for normally distributed variables
- Median and Inter-quartile Range (25th and 75th percentiles) for non-normally distributed variables

For number of events per year, the summary statistics include:

- Sample size (n)
- Count and Percentage by category (distribution): 0, 1, 2, 3 and ≥ 4

For other categorical variables, the summary statistics include:

- Sample size (n)
- Count and Percentage by category (distribution)

Characteristics are compared using the chi-squared test for categorical variables and a Student's t-test for normally distributed continuous variables or a Mann-Whitney test for non-normally distributed continuous variables.

3.4.1 Outcome analyses sub-study 1

Analyses will be performed in patients on different treatment regimens, adjusted for potential confounders (see paragraph 3.3.2) in two populations:

1. The full population of patients with COPD
2. A subpopulation of patients with "classical COPD" who had FEV₁/FVC <0.70 recorded within 5 years prior to the index date, never received an asthma diagnosis and have a smoking history

Negative binomial regression is performed to estimate RRs with 95% CI for the association between high blood eosinophil counts and the number of outcome events in the outcome period.

The primary definition of high blood eosinophil counts will be $\geq 0.45 \times 10^9/L$, based on previous work. Sensitivity analyses will be performed using ≥ 0.25 , $\geq 0.35 \times 10^9/L$ and $\geq 0.55 \times 10^9/L$ as cut-points.

Additional analyses will be performed to evaluate whether the MPR modifies the associations by including interaction terms of blood eosinophil counts and MPR into the regression model

(continuous or categorical depending on best model fit).

Analyses will be repeated in patients with good adherence, defined as $MPR \geq 80\%$.

Sensitivity analyses will be performed for the full population after exclusion of patients with any diagnostic Read code for asthma recorded ever.

Additional analyses will be performed to study whether the associations are different in never-smokers and ex-smokers in the full populations.

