Cox-proportional hazard regression with the time from hospital discharge date to the first re-admission date as the survival time, is performed to estimate HRs with 95% CI for the association between high blood eosinophil counts and time to re-admission over time periods

of 28 days, 12 weeks and 12 months, adjusted for potential confounders following the procedure as described for sub-study 1.

Table 1. Example of a life-table describing the time at hospital re-admission, by blood eosinophil count

Number of patients with high blood eosinophil count					Hazard probability	Survival probability
Weeks	At risk at start	Re-admission	Censored	Death		
4						
8						
12						
26						
36						
52						
Number of patients with normal blood eosinophil count					Hazard probability	Survival probability
Weeks	At risk at start	Re-admission	Censored	Death		
4						
8						
12						
26						
36						
52						
Total population					Hazard probability	Survival probability
Weeks	At risk at start	Re-admission	Censored	Death		
4						
8						
12						
26						
36						
52						

3.4.3 Outcome analyses sub-study 3

Means of the number of events per person year of follow up with standard deviations (SD) will be reported for count variables next to distributions (number and percentage) of categorical variables describing HRU in the baseline and outcome year. HRU events recorded at the index date are included in the baseline year, except medication prescriptions for which prescriptions at the index date are included in the outcome year.

Costs will be described as means with standard deviations. Costs of 4 subgroups of patients on Triple therapy at high risk of exacerbations will be compared with overall mean costs of patients with COPD in the total population by calculation of costs ratios with 95% confidence intervals, estimated by 1000 bootstrap replicates.

Non-parametric Mann-Whitney tests are performed to test differences in average costs between different populations of patients.

3.4.4 Outcome analyses sub-study 4

Two one or two-step generalized linear models with gamma distribution and log link will be used to perform regression analysis with total all-cause and total COPD-related costs as the outcome variables.

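### Sub-study 3's eosinophil cost contrast takes no account of asthma and sub-study 4 does so only in part, so some asthma cost may be credited to high eosinophils

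*Protocol*

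**What the plan says.** **Population.** Section 2.4, which covers all sub-studies, states: "Patients with a concurrent diagnosis of asthma will be included". Section 1.1 gives the reason this matters: "Eosinophilic inflammation is thought to be a characteristic feature of asthma rather than COPD".

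**Sub-study 1.** Section 3.4.1 states: "Sensitivity analyses will be performed for the full population after exclusion of patients with any diagnostic Read code for asthma recorded ever". It also analyses a classical COPD population that excludes anyone with an asthma diagnosis. Section 2.5.1 repeats the asthma-free analysis. No counterpart appears under sub-studies 3 and 4.

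**Sub-study 3.** The four subgroups are split by eosinophils and smoking only (2.5.3). Section 3.4.3 provides means, bootstrap cost ratios against the total population, and a test: "Non-parametric Mann-Whitney tests are performed to test differences in average costs between different populations of patients". No covariate is named. Section 3.6.3 sizes this sub-study for a 0.3 SD cost difference between high and normal eosinophil patients.

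**Sub-study 4.** Section 3.3.3 item 9a offers asthma as 'ever' only, while rhinitis and eczema each have three levels. Predictors are chosen by backward AIC selection, and the eosinophil cost ratio is adjusted for those that remain (3.4.4).

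**Confounding.** Section 3.3.2 lists asthma in three levels (never, active, ever but not active). Its heading refers to outcomes in general. Section 3.5.1 says that analyses will be adjusted for all potential confounders by multiple regression.

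**COPD-related use (3.2.4).** It includes "Number of A&E attendances for COPD or other lower respiratory conditions" and "Number of referrals to specialist for COPD or other lower respiratory conditions". Item 5, "Number of COPD-related drug prescriptions", lists inhaled and oral steroids, bronchodilators and theophylline by class. Only antibiotics need a lower respiratory code.

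**The concern.** Section 1.3 hypothesises that COPD costs are meaningfully higher with high eosinophils, above all in at-risk patients on triple therapy. Asthma is tied to eosinophilia on the protocol's own account, and it brings A&E visits, referrals and prescriptions of its own. If asthma is commoner in the high-eosinophil group, an unadjusted contrast mixes its cost with whatever belongs to eosinophilic COPD. The protocol saw this risk for exacerbations and checks it in sub-study 1. Costs, where the outcome definition itself can take in asthma care, get no such check in sub-study 3 and a weak one in sub-study 4. At stake is whether a higher cost can be read as the burden of an eosinophilic COPD phenotype.

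**Working it through.** **1. Control for asthma, by sub-study**

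| | Adjusted for asthma | Asthma-free repeat |
|---|---|---|
| 1 (3.4.1) | Three-level variable, 5% change-in-estimate rule | Yes, and classical COPD |
| 2 (3.4.2) | Same procedure as sub-study 1 | No |
| 3 (3.4.3) | None | No |
| 4 (3.4.4) | 'Ever' only, may be dropped by AIC | No |

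The row for sub-study 3 cannot be squared with 3.5.1.

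**2. The plan's sample sizes**

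Inputs: 0.3 SD and 0.2 SD, 80% power, alpha 0.05, 10% high eosinophils. The last three are stated in 3.6.4 and assumed to apply to 3.6.3. A two-sided test is also assumed. Total N = (1.960 + 0.842)² / (d² × 0.10 × 0.90).

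- d = 0.3: 7.849 / 0.0081 = 969, or 970 after rounding by group. Plan: 979.
- d = 0.2: 7.849 / 0.0036 = 2,180, or 2,182 after rounding by group. Plan: 2,200.

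Both are reproduced to within about 1%. A high-versus-normal contrast is therefore what sub-study 3 was sized for.

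**3. Possible size of the asthma effect in an unadjusted contrast**

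The documents give no asthma share by eosinophil group and no cost multiplier, so all inputs here are assumed. With asthma shares pH (high) and pN (normal), and asthma multiplying cost by k, the cost ratio from asthma alone is (1 + pH(k−1)) / (1 + pN(k−1)).

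| pH / pN | k = 1.2 | k = 1.5 |
|---|---|---|
| 25% / 25% | 1.00 | 1.00 |
| 40% / 30% | 1.08/1.06 = 1.02 | 1.20/1.15 = 1.04 |
| 45% / 30% | 1.09/1.06 = 1.03 | 1.225/1.15 = 1.07 |
| 50% / 25% | 1.10/1.05 = 1.05 | 1.25/1.125 = 1.11 |

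At k = 2.0, 50% versus 25% gives 1.50/1.25 = 1.20.

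For scale, if the SD of log cost is 0.8 to 1.2 (assumed), the 0.3 SD target is a ratio of exp(0.24) to exp(0.36), that is 1.27 to 1.43. The 0.2 SD target is exp(0.16) to exp(0.24), that is 1.17 to 1.27.

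**4. What an asthma-free repeat can deliver**

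High-eosinophil cells at N = 979, with 57% not smoking (3.6.3): 979 × 0.10 × 0.57 = 56 and 979 × 0.10 × 0.43 = 42, before asthma is removed.

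If a share f has asthma, power = Φ(d√(N(1−f) × 0.09) − 1.960). At N = 979, d = 0.3 and f = 30%: 0.3 × √61.7 = 2.36, and Φ(0.40) = 65%. Across f = 10%, 20%, 30%, 40% and 50%, power is about 76%, 71%, 65%, 59% and 51%. The figures for 2,200 and 0.2 SD are the same.

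**The case against.** Several points on the other side are sound.

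- **An imbalance would be seen.** Sections 3.3.1 and 3.4 tabulate asthma in three levels by comparison group, with chi-squared tests. A reader might infer that nothing in sub-study 3 would reveal the problem, and that is not so. The tables would show the imbalance; they would not show what it does to cost.
- **Sub-study 4 is not uncontrolled.** If asthma raises cost materially, AIC will tend to keep it. What remains is the coarse coding and the lack of any guarantee that the term stays.
- **Not all asthma care counts as COPD-related.** Admissions must carry J44.0 or J44.1, even under the wider item: "With COPD exacerbations ICD-10 J44.0 or J44.1 as secondary / subsidiary diagnosis and respiratory conditions (ICD-10 J00-J99) as primary diagnosis". GP visits must be COPD-related, and all-cause costs include asthma by design. Everyone in the sub-study 3 subgroups is on triple therapy, so use of those classes is common to both eosinophil groups. The point is confined to A&E attendances, referrals and drugs counted by class.
- **Objective 3 is largely descriptive.** Unadjusted means suit a broad real-life population, and the total-population comparator also contains asthma patients. This supports keeping those means as primary. It does not balance asthma between the high and normal groups, a contrast that 3.6.3 sizes.
- **The earlier exacerbation association was unaffected by an asthma record (1.1).** That was a finding on exacerbations in OPCRD, not on costs in CPRD with HES.
- **Asthma may lie on the causal pathway.** Section 3.4.1 gives this warning for comorbidities linked to eosinophils. It argues against making the asthma-free result primary, not against showing it.
- **Extra sensitivity analyses may sit in the SAP.** That is possible. But the protocol itself fixes sub-study 3 as unadjusted, against 3.5.1, and fixes item 9a as 'ever'.

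**Conclusion.** The point holds in a limited form. Sub-study 3's high-versus-normal cost contrast has no adjustment, stratum or sensitivity analysis for asthma, contrary to 3.5.1 and despite 3.3.2. Sub-study 4 has partial control.

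Extra cost from asthma may therefore be credited to high eosinophils. A reader might go further and conclude that it will be. The documents do not support that, because they show neither an imbalance in asthma nor its effect on cost. The ratios of 1.02 to 1.11 rest wholly on assumed inputs, fall to 1.00 with equal asthma shares, and lie below the cost differences that the plan is sized to find. They are still large enough to blur the reading of a modest cost ratio. This is an inexpensive improvement to interpretation, not a flaw that invalidates either sub-study.

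**What to change.** 1. Keep the full-population estimates as primary in both sub-studies.
2. In 3.4.3 and 3.4.4, add a sensitivity analysis in patients with no asthma Read code ever, the rule already used in sub-study 1. Apply it to the sub-study 3 cost contrasts and the sub-study 4 eosinophil cost ratio. Report estimates with confidence intervals, as a robustness check and not as a second test.
3. In 3.3.3 item 9a, replace 'Asthma ever' with the three-level variable of 3.3.1 and 3.3.2, and keep it in the model from which the eosinophil cost ratio is reported, whatever AIC selects.
4. Reword 3.5.1 so that it matches what sub-study 3 does: unadjusted primary estimates with an asthma-free check.

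This needs extra tables and one model constraint, from data already held. The price is precision: high-eosinophil cells start at about 56 and 42 before exclusions, and power at the stated N falls to about 65% if 30% have asthma (assumed). To retain 979 and 2,200 asthma-free patients at that share would take 979/0.7 = 1,399 and 2,200/0.7 = 3,143 patients. For a robustness check, wide intervals are acceptable.

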2.5 Study designs

2.5.1 Objective 1

The index date (ID) of objective 1 will be the most recent date of a recorded blood eosinophil count, measured at the time of stable disease, defined as no COPD exacerbation within 4 weeks prior to or at ID and no change in treatment regimen, ICS dosage and substance during the study period (Figure 1).

[figure not shown]

Figure 2. Study design objective 1

Patient's demographics and clinical characteristics will be described and potential confounders will be assessed in a baseline year prior to ID.

The association between high blood eosinophil counts (at ID) and (moderate or severe) COPD exacerbations in the subsequent year will be assessed in subgroups of patients defined by smoking status (active smoker in baseline year or not) and the following treatments in the baseline year (22):

1. Short-acting bronchodilators as required only (SABA and/or SAMA)
2. Maintenance therapy with LAMA and/or LABA
3. ICS / LABA in combination inhaler
4. Triple therapy: ICS + LABA + LAMA

The primary definition of "high eosinophil counts" will be $\geq 0.45 \times 10^9/L$, based on our previous work. Sensitivity analyses will be performed using 0.25, 0.35 and 0.55 as cut-points.

Sensitivity analyses will be performed in the subgroup of patients with COPD who have never been diagnosed with asthma, i.e., no diagnostic Read code for asthma recorded ever.

Additional analyses will be performed to evaluate whether the Medication Possession Ratio (MPR) for maintenance treatments (ICS / LAMA / LABA) modifies the associations by:

1. Including interaction terms of blood eosinophil counts and MPR into the regression model (continuous or categorical depending on best model fit) to explore whether MPR significantly modifies the association and at which values
2. Repeating analyses in patients with good adherence to ICS, using the widely used cut-point of $MPR \geq 80\%$ for therapy options 3 and 4

2.5.2 Objective 2

The ID of objective 2 will be the date of the most recent first discharge from hospital admission for COPD exacerbation occurring within one year after a blood eosinophil count measured at the time of no recent exacerbation (Figure 3). Patients will be followed after ID until re-admission or death to a maximum of one year after each index date.

The risk of COPD-related re-admission to hospital for COPD within 4 weeks and 1 year will be compared for patients with and without high blood eosinophil counts year prior to index date. All analyses will be adjusted for potential confounders in multiple regression analysis.

[figure not shown]

Figure 3. Study design objective 2

2.5.3 Objective 3

The ID of objective 3 will be the most recent blood eosinophil count recorded at the time of no recent exacerbation (Figure 4).

HRU and costs, broken down by type of utilisation and total costs will be assessed in both a baseline year prior to ID and a follow-up year (outcome year) after ID.

Mean all-cause and COPD-related HRU and associated costs will be estimated in one follow-up year after the eosinophil count in the following 4 subpopulations, defined in a baseline year, of patients with COPD on triple therapy, who are at high risk of exacerbations (i.e. a history of ≥ 2 exacerbations or ≥ 1 exacerbation leading to hospitalisation in the baseline year):

Patients with high blood eosinophil counts who are:

1. not actively smoking
2. actively smoking

Patients with normal blood eosinophil counts who are:

3. not actively smoking
4. actively smoking

Mean HRU and costs will be compared with values observed in the total population of patients with COPD who have blood eosinophil counts available.

Figure 4. Study design 2

[figure not shown]

Figure 4. Study design objective 3

2.5.4 Objective 4

The ID of objective 4 will be the most recent blood eosinophil count recorded at the time of no recent exacerbation with one baseline year prior to index date for assessment of potential predictors of costs.

Total all-cause and COPD-related medical costs will be assessed in the outcome year after ID (Figure 5).

Two multiple regression analyses will be performed with total all-cause costs and total COPD-related costs as outcome variables. All potential predictors will be evaluated as independent variables, including blood eosinophil counts and its interaction with smoking status.

[figure not shown]

Figure 5. Study design objective 4

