3. A. To estimate mean all-cause and COPD-related health care resource use (HRU) and associated costs in 4 subgroups of patients who are at risk of exacerbations (i.e. a history of ≥ 2 exacerbations or ≥ 1 exacerbation leading to hospitalisation in the past 12 months) while receiving treatment with triple therapy, where the 4 subgroups are defined by the presence or absence of high blood eosinophil counts and current smoking habits
B. to compare HRU and costs with those for the total population of patients with COPD who have blood eosinophil counts available
4. To study whether the presence of high blood eosinophil counts is associated with greater all-cause and COPD-related costs in the subsequent year and to study which other easily accessible characteristics drive future costs in patients with COPD

Methods:

Study design:

An observational historical cohort study will be performed among the UK population of patients with COPD who have blood eosinophil counts available.

Patients will be characterised in a baseline year prior to the index date (ID) and outcomes will be measured in the year after ID.

Data Sources:

Analyses for sub-study 1 (association between high eosinophil counts and COPD exacerbations) will be performed in patients from OPCR. A subpopulation of patients from CPRD with linkage to Hospital Episode Statistics (HES) available will be selected for sub-studies 2–4 (association between high blood eosinophil counts and the risk of hospital re-admission for COPD and study on HRU and costs)

Study Population:

The index date (ID) will be the most recent blood eosinophil count measurement, except for sub-study 2 for which the hospital discharge date of the most recent first hospitalization for COPD within one year after a blood eosinophil count measurement will be used as ID. Eligible patients should be ≥ 40 years old and have at least 1 year of continuous data prior to and after the respective IDs, except for sub-study 2 in which patients who die or who are lost to follow-up in the outcome year are censored. Patients eligible for sub-study 1 need to be on stable treatment during the study period.

Exposures:

Only eosinophil counts measured when there was no recent (4 weeks) exacerbation recorded are considered. The primary definition of high blood eosinophil counts will be $\geq 0.45 \times 10^9/L$, based on previous work. Sensitivity analyses will be performed using ≥ 0.25 , ≥ 0.35 and $\geq 0.55 \times 10^9/L$ as the definition.

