2.3 Inclusion Criteria

Overall inclusion criteria:

1. A diagnostic Read code for COPD³ qualifying for inclusion in the register of patients with COPD recorded after 1st April 2008 (21)
2. Age \geq 40 years at the most recent diagnostic code and at index dates
3. \geq 1 valid blood eosinophil count measured when there was no recent exacerbation recorded, i.e., within 4 weeks prior to or at the measurement
4. Valid continuous data in a baseline year prior to index date
5. At least one year of continuous outcome data after the index date, except for patients included in the study of objective 2, in which patients lost to follow up are censored

Objective-specific inclusion criteria:

6. Objective 1:
Stable COPD therapy, i.e. no change in treatment regimen, ICS dosage and substance during baseline and outcome years
7. Objective 2:
 - a. Hospital discharge of admission with COPD exacerbation as diagnosis
 - b. Blood eosinophil count measured at the time of no recent exacerbation within 1 year prior to ID
8. Objectives 2, 3 and 4:
Linkage to HES data available

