 - b. GOLD B: FEV₁ % predicted ≥ 50 and ≤ 1 COPD exacerbation and no hospitalization for COPD in baseline year and mMRC ≥ 2
 - c. GOLD C: FEV₁ % predicted < 50 or ≥ 2 COPD exacerbations or ≥ 1 hospitalization for COPD in baseline year) and mMRC 0–1
 - d. GOLD D: FEV₁ % predicted < 50 or ≥ 2 COPD exacerbations or ≥ 1 hospitalization for COPD in baseline year) and mMRC ≥ 2
 - e. Unknown
10. ICS/LABA combinations prescribed with dosages (most recent in the baseline year)
- a. Budesonide / formeterol (Symbicort[®] / DuoResp Spiromax[®])
 - b. Fluticasone propionate / salmeterol (Seretide[®])
 - c. Beclomethasone / formeterol (Fostair[®])
 - d. Fluticasone furoate / vilanterol (Relvar Ellipta[®])
11. Cumulative doses prescribed in the baseline year (expressed as average dose per day):
- a. Average cumulative ICS dose
 - b. Average cumulative SABA dose
 - c. Average cumulative SAMA dose

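### Sub-study 2 ends its baseline year at hospital discharge, so the index admission enters baseline history and some confounders can be recorded after the eosinophil count

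*Protocol*

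**What the plan says.** All references are to the protocol.

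- **Index date.** Section 2.5.2: "The ID of objective 2 will be the date of the most recent first discharge from hospital admission for COPD exacerbation", occurring within a year after a stable-state eosinophil count. The opening summary (Study Population) agrees. It uses the count as ID "except for sub-study 2 for which the hospital discharge date of the most recent first hospitalization for COPD" takes that role. For objectives 1, 3 and 4 the count date is the ID.
- **Baseline window.** The summary (Study design) states for the whole project: "Patients will be characterised in a baseline year prior to the index date (ID) and outcomes will be measured in the year after ID". Section 2.3 item 4 requires "Valid continuous data in a baseline year prior to index date". Item 5, directly below, makes an exception for objective 2, but only for follow-up.
- **Exposure.** Section 2.3 item 7b: "Blood eosinophil count measured at the time of no recent exacerbation within 1 year prior to ID".
- **GOLD groups (3.3.1 item 9).** A and B are closed to a patient with any "hospitalization for COPD in baseline year and mMRC" then separates A from B. One such admission is enough for C or D. There is also an Unknown group.
- **Adjustment.** Section 3.3.2 lists age, sex, smoking, BMI, asthma, rhinitis, eczema, nasal polyps and Charlson index. Section 3.4.2 applies the sub-study 1 procedure to the Cox model.

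**The concern.** In sub-studies 1, 3 and 4 the baseline year ends at the exposure. In sub-study 2 the same rule is attached to a date that comes after the exposure and after the event that qualifies the patient. The baseline year then contains both the count and the index admission.

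Three things are at stake:

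- The baseline table should show whether the high and normal eosinophil groups were similarly ill before the index event. Rows that the index admission itself fills do this poorly. Section 3.3.2 holds no exacerbation-history or lung-function variable, so readers will lean on that table.
- The adjusted hazard ratio may be conditioned on codes that arose after the count, as the index exacerbation developed.
- A count may be accepted as stable because the weeks before it were not observed. Section 3.1.1 says the earlier work found lower counts after recent oral steroid courses, so such a count could be misclassified.

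**Working it through.** **The plan's own figure.** The only computed figure for sub-study 2 is Table 3. With the Freedman log-rank formula, two-sided alpha 0.05 (the protocol does not state sidedness), 80% power, HR 1.3 and φ = 999/9,080 = 0.110:

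- Events = (1.960 + 0.842)² × (1 + 0.110 × 1.3)² / (0.110 × 0.3²) ≈ 1,036.
- Risk in the high group = 1 − 0.9^1.3 = 0.128. Mean risk = (0.10 + 0.110 × 0.128)/1.110 = 0.1028.
- N ≈ 1,036/0.1028 ≈ 10,077 without intermediate rounding, against 10,079 stated.

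Table 3 reproduces, and nothing below changes it. The rest is a reading of date windows.

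**Step 1: the index admission.** An admission precedes its own discharge, so it lies in the year ending at discharge. No sentence removes it. Every patient then has at least one COPD hospitalisation at baseline, provided that the uncoded GOLD term for a COPD hospitalisation covers J44.0 or J44.1 in any diagnostic position, as section 3.2.2 does for the index event. GOLD A and B are then empty. Patients with a recorded mMRC are C or D, and the others are Unknown. GOLD, exacerbation history and prior admissions are absent from 3.3.2, so none of this reaches the Cox model.

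**Step 2: the confounders.** The count is up to 365 days before ID, so anything dated by ID or by the baseline year can fall after it.

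| Variable | Dating rule (3.3.1) | Can it postdate the count? |
|---|---|---|
| Sex | none | No |
| Age | at ID | Shifts by at most one year |
| Active asthma, rhinitis, eczema | diagnosis in the baseline year, or earlier diagnosis plus a prescription in that year | Yes, directly |
| Smoking | code nearest to ID, 5-year look-back | Yes, if re-coded after the count |
| Charlson, nasal polyps | diagnosis at any time before ID | Yes, for new diagnoses |
| BMI | up to 10 years before ID | Yes, if re-measured |

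For example, a prescription issued as the index exacerbation develops could move asthma from *ever, not active* to *active*.

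**Step 3: the stability look-back.** For a count d days before discharge, the 28-day look-back reaches day d + 28. It is fully inside the required 365 days only if d + 28 ≤ 365, that is d ≤ 337. Dates 338 to 365 fail: 365 − 337 = 28 dates, and 28/365 = 7.7% of eligible dates. At d = 338 one day is uncovered. At d = 365 all 28 preceding days are. The furthest reach is 365 + 28 = 393 days, so a patient whose records go back at least 393 days before discharge is never affected.

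**The case against.** The strongest reply is that describing patients at discharge is reasonable for a re-admission question. Discharge is time zero, covariates are current there, and in a cohort selected on a COPD admission the presence of one is an entry criterion common to both groups. FEV₁, mMRC, comorbidity and the number of events beyond the index one still vary. This stands in part. It defends describing patients at discharge, but not counting the qualifying event as prior history or adjusting for codes that may follow the exposure.

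Section 3.4.1 already recognises that comorbidities may lie on the causal pathway and has effects of 5% or more on the estimate reported separately, and 3.4.2 adopts that procedure. This helps, but only partly. It shows how far an adjustment moves the hazard ratio, not whether the code came before or after the count, and it does not cover smoking.

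The objective 2 design figure is not shown and could draw the window differently, but the text gives no exception.

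Stronger readings that the documents do not support:

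- *Every patient is GOLD C or D.* Unknown exists, and the coding of the hospitalisation term is an assumption.
- *The GOLD problem biases the hazard ratio.* GOLD is descriptive only.
- *All confounders are measured after the exposure.* Some can be, and many values will predate the count. Comorbidities are defined by Read codes, while admissions carry ICD-10 codes, so capture during the stay itself is not shown.
- *7.7% of counts are misclassified.* It is a share of dates, and it matters only where records start about 12 to 13 months before discharge.
- *The index-date footnote in 3.2.4 creates the problem.* Its rule, "Events occurring at index date are counted in the baseline year", concerns resource use and is not needed for the argument.

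**Conclusion.** The point holds as a low-cost improvement, not as an error that invalidates sub-study 2.

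- Baseline history includes the index admission on the written definitions. GOLD A and B are empty, given the coding assumption in step 1. The harm is to the baseline description.
- The hazard ratio may be adjusted for post-exposure information through a limited set of covariates. The documents give no distribution of count-to-discharge times or of coding dates, so neither the direction nor the size of any bias can be stated.
- The stability check is not guaranteed for 28 of 365 eligible count dates. The number of patients concerned depends on how far records extend beyond the required year, which is a minimum and not a cap, and is probably small.

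**What to change.** For objective 2, in sections 2.3 and 2.5.2:

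1. Exclude the index admission from the baseline hospitalisation, exacerbation and GOLD variables.
2. Date time-varying confounders (active asthma, rhinitis and eczema, smoking, BMI, Charlson diagnoses) at or before the qualifying count, and at the latest on the day before the index admission.
3. Require continuous records covering at least the 28 days before the count.
4. Keep discharge as time zero for follow-up.

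This takes a few sentences and a changed date anchor in the code, set before analysis. Patients without records for the look-back are lost, probably few. Some covariates will be older at discharge, by a gap that varies between patients. Moving the whole baseline description to the count date is partly a matter of preference. The four changes above do not require it, and characteristics at discharge can still be tabulated alongside.
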